## LET Comparison Study

Revised: June 22, 2016

The investigator will interview for demographic data, ensure proper application of LET gel according to randomized group, observe laceration repair, record use of additional anesthesia, (including all data collection on data form).

Describe procedures taken to lessen the probability or magnitude of risks.

Risks to the patient are minimal given that LET is routinely used in the pediatric ED and has been shown to be efficacious. To minimize risk, patients and/or clinicians can withdraw from the study at any time.

Identify which procedures are being done as part of the Human Research and which are being conducted anyway for other reasons.

The randomization to the timing and number of applications of LET gel is being done specifically for this study as are the VAS post placement of first suture. Repair of the laceration will be done as part of standard of care.

Describe all drugs and devices used in the research and the purpose of their use, and their regulatory approval status.

LET gel is compounded by our pharmacy using the formula shown in Appendix 2.

Describe the source records that will be used to collect data about subjects. Attach all surveys, scripts, and data collection forms.

The attached survey forms can be seen in Appendices.

Describe what data will be collected including long-term follow-up.

There will not be any long-term follow up.

### a) Data and Specimen Banking\*

If data or specimens will be banked for future use, describe where the specimens will be stored, how long they will be stored, how the specimens will be accessed, and who will have access to the specimens.

We are not banking data for future sharing or use.

List the data to be stored or associated with each specimen.

N/A

Describe the procedures to release data or specimens, including: the process to request a release, approvals required for release, who can obtain data or specimens, and the data to be provided with specimens.

We are not banking data for future sharing or use by outside researchers.

### b) Data Management \*

Describe the data analysis plan, including any statistical procedures.

Provide a power analysis.

The study hypothesis is that there will be at least a 1 point difference in pain score. Sample size is calculated such that the study will have a power of 90% to detect a 1 point difference in pain scores using a two sample t test with an alpha of 0.05.

Describe the steps that will be taken to secure the data (e.g., training, authorization of access, password protection, encryption, physical controls, certificates of confidentiality, and separation of identifiers and data) during storage, use, and transmission.

Original data forms and consent forms and scales will be kept in a locked office. We will not record any identifiers as defined by HIPAA on our data forms and scales. We will assign a random unique study identification number to each subject and this number will be used rather than the subject's name on the data forms and in our database/excel spreadsheets. We will not maintain a link between the study ID number to each individual; however will still seek individual permission to collect and use protected health information using a PHI authorization.

Data will be entered into password protected excel files and analyzed using SAS statistical analysis software. Excel files will be de-identified using study numbers; no patient names or identifiers will remain. Study numbers will be used to enter into excel files. Only the study investigators will have access to the data forms and files. All investigators will be trained in confidentiality, CITI training.

Data will be kept for at least 3 years after completion of the research. This includes data collection forms, consent documents, etc. We will ensure that all data is de-identified at that time.

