### Secondary outcomes:

- 1) To compare provider satisfaction scores using a Likert scale between the triple LET and single LET application techniques.
- 2) To compare parental satisfaction scores using a Likert scale between the triple LET and single LET application techniques.
- 3) To compare the need for additional local anesthetic infiltration between the triple LET and single LET application techniques.

**Hypothesis:** We believe that applying LET gel 3 times over a 30 minute period will provide superior anesthesia to one 30 minute long application.

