## 7) Resources Available to Conduct the Human Research

Justify the feasibility of recruiting the required number of suitable subjects within the agreed recruitment period. For example, how many potential subjects do you have access to? What percentage of those potential subjects do you need to recruit?

We are a county hospital with a Pediatric ED, level 1 trauma center that sees ~24000 patients aged < 21 years annually. Of these there are a number who will present with a laceration requiring repair.

We will be studying a convenience sample of patients requiring simple laceration repairs; enrollment will be centered around availability of investigators.

Sample size calculations revealed that enrolling 22 patients per group would have 90% power to detect a 1 point difference in visual analog pain score (range 0-10) between groups with a standard deviation of 1, using a two sample t test with an alpha of 0.05. We estimate that the enrollment will be complete within 1 year after IRB approval.

Describe the time that you will devote to conducting and completing the trial within the agreed trial period.

The Principal Investigator will devote ~5 hours a week/month to conducting this study. The fellows involved will devote ~20 hours a week/month.

Describe the number and qualifications of your staff, their experience in conducting research, their knowledge of the local study sites, culture, and society.

We will have 2 fellows enrolling patients in the Pediatric ED.

Drs. [name], [name], and [name] developed the study design and will be involved in data collection, analysis, and manuscript preparation.

All members of the research team have completed CITI training. The team includes:

**[name] MD, MS, FACEP, FAAP:** [name] is a pediatric emergency medicine fellowship trained Clinical Professor of Pediatrics, the pediatric emergency medicine fellowship director, and has a Master of Science in Epidemiology and experience in research regarding pain with procedures. She is a reviewer for eight journals, an associate editor for Annals of Emergency Medicine, has been principal investigator or co-investigator on several projects including as recipient of a K23 award. She has coauthored 13 peer-reviewed manuscripts.

**[name]:** [name] is a pediatric emergency medicine fellow with prior research experience. He completed his residency in pediatrics. He anticipates completing his fellowship in June 2017.

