### **f) Study Endpoints\***

Describe the primary and secondary study endpoints.

Describe any primary or secondary safety endpoints.

**Primary endpoint:** To compare pain scores during laceration repair with first suture placement using standardized visual analog scale (VAS) between 2 different topical local anesthetic application techniques for using LET gel. Specifically, we are looking to see if applying LET gel 3 times, spaced 10 minutes apart (triple LET) provides superior anesthesia to one 30 minute application (single LET).

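### Does wording the hypothesis as a difference of one point or more undermine a t test planned and powered against zero difference?

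*Combined protocol and SAP*

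**What the plan says.** The hypothesis appears in two forms.

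- **Section 4) Objectives**, under the label Hypothesis: "We believe that applying LET gel 3 times over a 30 minute period will provide superior anesthesia to one 30 minute long application". The primary outcome in the same section and the primary endpoint in section 9 f) Study Endpoints frame the comparison in the same way. All three ask whether triple LET is better than single LET, and none sets a margin.
- **Section b) Data Management**, in reply to the template's prompts for an analysis plan and a power analysis: "The study hypothesis is that there will be at least a 1 point difference in pain score". The next sentence sizes the trial so that "the study will have a power of 90% to detect a 1 point difference in pain scores".

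Section 7) Resources gives the sample-size inputs: "enrolling 22 patients per group would have 90% power to detect a 1 point difference", "between groups with a standard deviation of 1", "using a two sample t test with an alpha of 0.05". Section 9 c) Local Number of Subjects repeats 22 per arm, 44 in all. No section states a null value, whether the test is one- or two-sided, a success criterion, or a rule for interpreting a confidence interval.

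**The concern.** Read literally, the Data Management sentence is a minimum-effect hypothesis: the true difference is one point or larger. A t test against zero cannot establish that. It can be significant when the observed difference is well short of a point, and the 90% power does not apply to a one-point null.

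The fear is that a significant p-value could be reported as confirming a one-point benefit, because that is what the analysis section calls the study hypothesis. The department hopes to learn whether to change its application method (section 20), so the gap between some benefit and a benefit of at least a point would matter to readers.

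**Working it through.** **Inputs.** Difference 1 point, SD 1, alpha 0.05, two-sample t test, 22 per group (section 7; section 9 c). A two-sided test is inferred in step 1.

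**1. Reproduce the plan's figure with a null of zero.** Normal approximation:

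n per arm = 2 × (1.960 + 1.282)² × SD² / difference² = 2 × 10.51 × 1 / 1 = 21.01, rounded up to 22.

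Exact noncentral t with 42 degrees of freedom: two-sided power 89.97%. One-sided alpha 0.05 would give 94.7%, so the stated 90% matches a two-sided test of zero difference.

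**2. Smallest significant observed difference.**

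SE = SD × √(2/22) = 0.3015. Threshold = 2.018 × 0.3015 = 0.608.

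An observed 0.61 gives p = 0.0495 and a 95% CI of 0.61 ± 0.608, that is 0.00 to 1.22. It just excludes zero and includes 1. This depends on the observed SD: the threshold is 0.91 at SD 1.5 and 1.22 at SD 2 (both SDs assumed).

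**3. What the design would do against a null of one point.** The whole 95% CI must lie above 1, so the observed difference must exceed about 1 + 0.608 = 1.61. True differences above 1 are assumptions; the documents give none. SD is 1.

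| True difference | Chance that CI lies wholly above 1 (22 per arm) | n per arm for 90% power against a null of 1 |
|---|---|---|
| 1.00 | 2.5% | not attainable |
| 1.25 | 12.5% | 21.01 / 0.25² → 337 |
| 1.50 | 36.7% | 21.01 / 0.5² → 85 |
| 2.00 | 90.0% | 21.01 / 1² → 22 |

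At a true difference of 1, 90% of trials reject zero and 2.5% have an interval wholly above 1. Hence 1 − 0.025/0.90 = 97% of the significant trials have an interval reaching below 1. In simulation about 44% of those significant trials observe less than 1 point. At an assumed true difference of 0.5, 37% of trials are significant, and 87% of those observe less than 1 point.

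**4. Which hypothesis did the plan adopt?** Three statements in the objectives and endpoints give superiority without a margin. Both figures in the sample-size statement, 22 and 90%, fit a null of zero. Against a null of 1, 22 per arm would give 90% power only if the true difference were about 2, a value that appears nowhere. The power claims speak of detecting one point, which is correct for a test of zero when the true difference is one. Only one sentence points the other way. It opens the reply that contains the power analysis and is followed at once by the power claim, so it reads naturally as naming the planning difference.

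**The case for a change.** The case for a change is this. Data Management is the only section that answers the prompt for an analysis plan, and the hypothesis written there is not the one the test addresses. It also gives no direction, whereas the Objectives do. With no success criterion and no interval rule, nothing formally prevents authors from choosing the stronger reading once the data are in. Rewriting would take two or three sentences and affect no patient.

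Part of this stands. The sentence is loosely worded, and a significant result near 0.61 would not by itself show a one-point benefit.

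The predicted consequence does not stand. The absence of a decision rule cuts both ways: a plan that never says when a one-point benefit will be claimed has not committed anyone to claiming it from p < 0.05. Nor can it be said without conditions that most significant results would fall short of one point. That depends on the unknown true difference (at 2.0, 90% of trials have an interval wholly above 1) and on the SD (at an observed SD of 2, every significant result has a point estimate above 1, though intervals could still reach below it). Finally, a rule reserving the one-point claim for intervals wholly beyond 1 would govern a claim that the plan does not set out to make.

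**Conclusion.** No change is needed. The arithmetic behind the worry is right, but it tests the plan against a minimum-effect design that it did not adopt. Followed as written, the plan gives a valid two-sided test of zero difference with 89.97% power at a true difference of 1 point and SD 1. A significant result favouring triple LET supports the superiority hypothesis stated in the Objectives. The mean difference and its interval come from the same t test, and a competent analyst would report them and let readers compare them with one point.

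What remains is a clerical looseness in one sentence. Tidying it would be harmless but would alter no analysis, number or sound conclusion.

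This rests on the test being two-sided, as the reproduced power indicates, and on the sponsor seeking superiority without a margin, as the Objectives and Study Endpoints say. If the sponsor did intend to demonstrate a benefit of a point or more, the one-point null would apply, and 22 per arm would suffice only for a true difference of about 2 points.

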### Describe the criteria that define who will be included or excluded in your final study sample.

#### Inclusion Criteria:

- Patients with simple ( $\leq 3$  cm) lacerations who are  $\geq 7$  years old and  $\leq 18$  years old, for whom the physician plans to close the laceration using simple superficial interrupted sutures.

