### **g) Procedures Involved in the Human Research\***

Describe and explain the study design.

Provide a description of all procedures being performed and when they are performed, including procedures being performed to monitor subjects for safety or minimize risks. Include procedures being performed already for diagnostic or treatment purposes and differentiate between these and the procedures performed solely for the research.

Once patients are identified and consent is obtained, they will be randomized to one of two groups. One group will have LET gel applied to the laceration one time for a duration of 30 minutes. The other group will have LET gel applied 3 times, at 10 minute intervals. Between applications, the excess gel on the surface of the skin will be gently wiped off, and a new strip of LET gel will be applied. The laceration repair will proceed in a normal sterile fashion, using standard irrigation and debridement techniques. Laceration repair will occur within the 15 minutes following the 30 minute period of LET application to the wound. The patient will be asked to rate his/her pain immediately after the first suture is placed or attempted using the visual analogue scale (VAS, range 0-10). The decision to use any additional anesthetic infiltration will be left to the performing provider. There will be 2 nurses involved in the study. One nurse will be the patient's primary nurse and will be administering the LET gel (so will not be blinded, but will not be involved in data collection). The other nurse will be obtaining the VAS immediately (Appendix 3) after the first suture is placed, using a pre-prepared script (Appendix 3) and standardized technique. The nurse or research assistant will also be blinded as to the method of LET gel application. The provider performing the laceration repair will be blinded. The research assistant will not be blinded and will coordinate all involved providers and nurses, will ensure correct timing in LET gel administration, and laceration repair timing.

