**Subjects who are not yet adults (infants, children, teenagers)**

- Describe the criteria that will be used to determine whether a prospective subject has not attained the legal age for consent to treatments or procedures involved in the Human Research under the applicable law of the jurisdiction in which the Human Research will be conducted. (E.g., individuals under the age of 18 years.)
  - For research conducted in the state, review “SOP: Legally Authorized Representatives, Children, and Guardians (HRP-013)” to be aware of which individuals in the state meet the definition of “children.”

Parental permission will be obtained from:

- One parent even if the other parent is alive, known, competent, reasonably available, and shares legal responsibility for the care and custody of the child.

Permission will be obtained from individuals other than parents if they are the legal guardians with documentation supporting this and not foster parents.

Assent will be obtained on all patients enrolled in the study. All patients will be at least 7 years old.

Assent will be documented with the child's signature (in writing) on the prepared and approved assent form.

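### First-suture VAS is to be compared by an unadjusted t test; adjusting for age is a cheap option, worth -0.8 to +4.7 points of power if age explains 0 to 20% of the variance

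*Combined protocol and SAP*

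**What the plan says.** Two places name a test for the primary outcome, both inside power statements. Section 7 (Resources Available to Conduct the Human Research) sets 22 per group for 90% power to detect a 1-point difference "with a standard deviation of 1, using a two sample t test with an alpha of 0.05". Data Management answers the request for an analysis plan with the same calculation, again "using a two sample t test with an alpha of 0.05", and later names SAS as the software. No covariate, model or stratification factor appears anywhere.

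The outcome is measured "using the visual analogue scale (VAS, range 0-10", immediately after the first suture. The inclusion criteria in section 9(b) admit children aged 7 to 18, and section 15 repeats the lower limit: "All patients will be at least 7 years old". Section 9(g) puts randomization after eligibility and consent: "Once patients are identified and consent is obtained, they will be randomized to one of two groups". It also says: "The investigator will interview for demographic data". On identifiers, Data Management states: "We will not maintain a link between the study ID number to each individual".

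**The concern.** Age is an eligibility variable with a wide range, it is fixed before allocation, and it probably falls under the interviewed demographic data. If older and younger children score pain differently, an unadjusted t test leaves that variation in the error term. A linear model with age would remove it and narrow the confidence interval without enrolling anyone else.

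Chance imbalance is a related point. With 22 per arm and no stratification described, the arms can differ in age. The t test is unbiased over repeated randomizations, but in the one trial that is run, an age gap would shift the estimate if age predicts pain.

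There is also a practical deadline. Since no link from study number to child is kept, age that is not written on the form at enrollment cannot be recovered at analysis.

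**Working it through.** **Inputs from the protocol.** n = 22 per arm, difference 1 point, SD 1, alpha 0.05 (sections 7 and 9(c), Data Management). Sidedness is not stated. Two-sided is used because it reproduces the stated power; one-sided 0.05 would give 94.7%. Complete data are assumed.

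**Assumed input.** R², the share of within-arm VAS variance explained linearly by age, is not in the documents. The range 0 to 0.20 is shown.

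**1. The plan's own figure.** SE = 1 × √(2/22) = 0.3015; noncentrality = 1/0.3015 = 3.317; df = 42. Noncentral-t power = 89.97%. The stated 90% reproduces.

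**2. Age-adjusted model.** One degree of freedom is lost (df = 41). The variance is multiplied by (1 − R²) and by 1 + 1/40, the average cost of chance age imbalance:

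Variance = SD² × (1 − R²) × (2/22) × (1 + 1/40)

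| R² | Noncentrality | Power | Change (points) | 95% CI half-width | Equivalent n per arm, t test |
|---|---|---|---|---|---|
| unadjusted | 3.317 | 90.0% | – | 0.61 | 22 |
| 0 | 3.276 | 89.2% | −0.8 | 0.62 | – |
| 0.05 | 3.361 | 90.7% | +0.7 | 0.60 | 22.5 |
| 0.10 | 3.453 | 92.1% | +2.1 | 0.58 | 23.7 |
| 0.20 | 3.663 | 94.7% | +4.7 | 0.55 | 26.6 |

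The half-width is t(0.975, df) × SE, with t = 2.018 at 42 df and 2.020 at 41 df. Power is equal for the two analyses at R² = 0.0255, a correlation of √0.0255 = 0.16. Integrating exactly over the distribution of age imbalance gives 89.2 / 90.7 / 92.1 / 94.7%, so the average factor is adequate.

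**3. Unlucky age imbalance.** Given an age imbalance with t statistic t, the variance factor is 1 + t²/42. At t = 2 it is 1 + 4/42 = 1.095. With R² = 0, power is 87.2%, a loss of 2.8 points. The chance of |t| > 2 is 5.2%. The gap is 2 × 0.3015 = 0.60 SD, or about 2.1 years if whole-year ages are uniform on 7 to 18 (SD 3.45). If age does predict pain, the same gap moves the unadjusted estimate by 0.603 × √R² points: 0.13, 0.19 and 0.27 at R² 0.05, 0.10 and 0.20.

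**4. Larger SD.** Same formulas:

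| SD | Unadjusted | R² 0 | R² 0.10 | R² 0.20 |
|---|---|---|---|---|
| 1.5 | 57.9% | 56.9% (−1.1) | 61.3% (+3.4) | 66.4% (+8.5) |
| 2 | 36.7% | 36.0% (−0.8) | 39.2% (+2.5) | 43.2% (+6.5) |

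**5. Bounded scale.** VAS scores may pile up at 0, so a floor-limited case was simulated. All its settings are assumptions: latent mean 1.5, latent SD 1.2, latent shift 1.31, scores clipped to 0–10 and rounded to 0.1, ages uniform, 60,000 trials per cell. About 11% of single-LET and 45% of triple-LET scores are 0, and the observed difference is 0.98. Adjustment changes power by −0.6 / +0.5 / +1.5 / +3.8 points at latent R² 0 / 0.05 / 0.10 / 0.20. Type I error is 5.0 to 5.1% for both analyses.

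**The case against.** The strongest reply is that nothing is broken: the t test is valid, unbiased and correctly powered for its inputs, so this is a preference for a covariate-adjusted model. That is right, and it is why the point is optional.

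The second reply is that the benefit hangs on an R² the documents do not give. The full 4.7 points needs a correlation of about 0.45 (√0.20). At R² 0.05 the gain is half a child per arm, and below a correlation of 0.16 adjustment loses power. This stands too, and it limits the claim to a conditional, modest gain. Against it, the range already charges adjustment for the lost degree of freedom and for chance imbalance. The average loss is at most 0.8 points.

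Third, age is not singled out in the protocol as prognostic; wound length and body site also vary and are also known before allocation. True. Age is the convenient choice because it is recorded on a natural scale and needs no new definition, but the documents do not show that it is the best covariate.

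Finally, the data form is not in the supplied text and age is very likely on it. The request is therefore to confirm the field, and no gap in the form is alleged.

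**Conclusion.** The point holds as a low-cost, optional improvement. With SD 1, a 1-point difference, 22 per arm and complete data, adjusting for age changes power by −0.8 to +4.7 points over an assumed R² of 0 to 0.20. The best case is worth about 4.6 extra children per arm (26.6 − 22). The worst average case costs 0.8 points, or 2.8 points with an age imbalance of t = 2.

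The result rests on an age–pain relation that the documents do not establish and on that relation being roughly linear. Adjustment does not rescue an underestimated SD: at SD 2 and R² 0.20, power is still 43.2%. Formally declaring a primary analysis would be useful in its own right, but that benefit is separate and is not counted here.

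**What to change.** Add one sentence to Data Management: *The primary analysis is a linear model of first-suture VAS on treatment arm and age in years (continuous), reporting the adjusted mean difference (triple minus single LET) with its 95% confidence interval; the unadjusted two-sample t test is a sensitivity analysis.*

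Before the first child is enrolled, confirm that the data form has a field for age in years.

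The cost is that sentence and, if the field is absent, one entry on the form. No patients or procedures are added. The price to accept is the small loss of power if age proves unrelated to pain.
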